9. EFFICACY ANALYSES

All efficacy analyses will be provided for the ITT Population. All efficacy analysis will be done using both the central radiology and local (i.e., investigator) assessment. Kaplan-Meier plots will be generated for all time-to-event analyses (i.e., for the Time to Progression, Progression-Free Survival, Duration of Response).

9.1 Primary Efficacy Analysis

The primary efficacy endpoint will be ORR as determined by the Investigator by using revised IWG response criteria for malignant lymphoma [4]. The final ORR for each subtype will be the rate of patients who met the ORR definition at the end of either the second or third cycle or during the follow up period (best response) (i.e the ORR will be derived from the variable “overall best response”). The denominator for calculating the rate will be based upon the total number of patients in the ITT population, thus patients without any post baseline assessment of NHL response will be included as non-responders. Overall ORR, independent of NHL subtype, will also be summarized. Exact (Clopper-Pearson) 95% CIs for ORR for each subtype and over all subtypes will be presented.

In addition, the tumor response categories will be evaluated by visit. The corresponding number of patients in each of the response categories will be summarized in a frequency table by visit. In this summary all patients who had discontinued will be analyzed as missing for all visits after study discontinuation, also accounting for all patients in the ITT population in the denominator.

ORR will be also calculated and respective results provided based on the central review assessment (based on the variable “best overall response”).

Sensitivity analysis:

The ORR will be calculated only considering patients who had at least on post-baseline response assessment. The analysis will be done using the local (investigator) assessment, and also based on the central review assessment.

Concordance rate:

The concordance rate in terms of response assessment represents the agreement in the best overall response between the central read and investigator assessment. The concordance rate is the number of patients that are concordant over the total number of patients assessed, and will be calculated across all response categories. A confusion matrix will be generated. The

concordance rate is calculated by adding the diagonal counts and dividing by the total number of patients assessed. Moreover, the agreement (%) of the investigator assessment with the central read in terms of best ORR will be calculated (i.e., the total number of patients with a best response of CR or PR by central review divided with the total number of patients with a best response of CR or PR by investigator assessment multiplied by 100).

Patients without any post-baseline response assessment will be considered as not evaluable (NE) in both the central read and investigator assessment. Patients who have been evaluated by investigator assessment, but not by central review assessment will be excluded from the concordance analysis.

The proportion (%) of patients who had at least one central review among the total number of patients who underwent at least one investigator assessment will be calculated. Moreover, the proportion (%) of the total number of central reviews among the total number of investigator assessments will be derived (i.e., the total number of central reviews across all visits and all patients divided with the total number of investigator response assessments across all visits and all patients multiplied by 100). The analysis will be conducted using the ITT population.

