5. SAMPLE SIZE DETERMINATION

A two-stage design is used to minimize exposure of NHL subtypes not showing responsiveness to MOR00208. No formal sample size estimations for determination of futility were computed for Stage 1. The number of patients to be used in this stage was determined to be the minimum number needed to adequately determine futility in any specific NHL subtype. The entire study will enroll between 40 to 120 patients, dependent upon patient response in each subtype in Stage 1.

Stage 1: Approximately 40 patients, an equal number of patients will be enrolled per NHL subtype:

- FL: 10 patients
- DLBCL: 10 patients
- MCL: 10 patients
- other indolent NHL: 10 patients

Observing less than two responses (at least PR) in 10 patients in any NHL subtype will be the criterion for discontinuing evaluation of MOR00208 in that NHL subtype. If the study drug is effective with a true ORR of 30%, the probability to stop for futility after the first stage for a specific NHL subtype is only 14.9%.

Stage 2: For those NHL subtypes with two or more responders, an additional 20 patients will be

enrolled for a total of 30 patients per subtype. Assuming that the true ORR of any NHL type is 30% and that the number of responses actually observed in the study corresponds to the expected number of responses (9 responses), N=30 would yield a lower limit of the 95% confidence interval for the ORR of 14.7%. Up to a maximum of 80 additional patients, an equal number of patients will be enrolled per “responding” NHL subtype. Some of the cohorts may have been stopped for futility after Stage 1:

- FL: 20 patients
- DLBCL: 20 patients
- MCL: 20 patients
- other indolent NHL: 20 patients

Approximately 25 to 30 centres in the United States of America and Europe are planned.

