7.3.4 Efficacy

7.3.4.1 Investigator Assessment

The Investigator will assess tumor response at specific study visits according to the criteria for NHL as defined in Section 17.4 of the study protocol. All of the criteria are based on the revised IWG response criteria [4].

The categories of overall tumor response assessment of the Investigator are as follows:

- CR - Complete remission
- PR - Partial remission
- SD - Stable disease

- PD - Progressive disease
- Missing (if response assessment is not done)

In case of progressive disease, the date of progression is given by the Investigator. In case any anti-tumor treatments other than MOR00208 are given before end of study (see also section 8.3), it is regarded as protocol non-compliance. Following a conservative approach, tumor assessments of the Investigator after start of other anti-tumor treatment which are non-PD will not be taken into account for any of the derived efficacy variables described below, whereas assessments of PD will still be taken into account. This ensures that a progression is still included in the analysis if an anti-tumor treatment has been started based on clinical progression, but the image confirming PD was done at a later time point. A response assessment provided by investigator after start of other than protocol indicated anti-tumor treatment will, however, not be counted for overall best response.

Tumor Response categories (Investigator) will be evaluated in terms of absolute and percentage frequencies by visit.

Overall best response (Investigator) will be defined as best response across the following time points: end of the second, end of third cycle, during a response assessment in the follow-up period or at an unscheduled assessment after end of second cycle.

Overall response rate (ORR) (Investigator) will be evaluated as the rate of patients who met the criteria of PR or CR at the end of either the second or third cycle or during a response assessment in the follow-up period (i.e. who have an overall best response of PR or CR).

Overall rate of SD (disease control rate) (Investigator) will be evaluated as the rate of patients who met the criteria of PR, CR or SD at the end of either the second or third cycle or during a response assessment in the follow-up period (i.e. who have an overall best response of PR, CR or SD).

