7.3.4.2 Central Read

Additionally a central radiology read of scans will be performed by SYNARC/BioClinica. The revised IWG criteria definitions [4] will also be applied. Details of the central read are described in the Independent Review Charter, Version 1.0, 01-JUL-2013, provided by SYNARC.

The independent reviewers (two primary radiologists) will be presented with all time points sequentially in chronological order, and will provide assessments for each time point. For the

overall tumor assessment of the central read a slightly different terminology is used:

- CR - Complete response
- PR - Partial response
- SD - Stable disease
- PD - Relapsed or progressive disease
- NE - Non-Evaluable (can be applied if repeated measurements cannot be applied for reasons such as inadequate or missing imaging and when progression/relapse cannot be assigned for the visit overall response)
- ND - No Disease (this category is used if there is no tumor and there was no tumor at baseline)

Once the independent reviews for all time points in the course of the study have taken place, all time points for a particular patient will be again reviewed together by the two independent reviewers in a global patient review over all time points. In their global patient review the two independent reviewers will determine:

- best overall response (defined as best response the subject had since treatment started taking into account scheduled and unscheduled visits)
- date of the best overall response
- duration of best overall response (calculated by the system as time from first response to progression if patient is PD at a specific visit)
- date when progression/relapse occurred

Finally, an adjudicator radiologist will perform adjudication, in case there is any discrepancy in the global patient review of the two primary radiologists. The adjudicator will review both initial readings and will record a new review that will agree with either of the duplicate reviews. Thus, the adjudicator will need to agree to the complete reading of one of the primary radiologists (all assessments by visit and all variables from corresponding global review). A mandatory comment will need to be recorded. The adjudicated reading results will be considered as the results for the involved patients.

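### The SAP's agreement percentage divides central by investigator responder counts, so it ignores overlap, can exceed 100% and can rise as agreement falls

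*SAP*

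**What the plan says.** The primary endpoint is ORR as judged by the investigator (SAP 2.2.1 and 9.1), in a single-arm, open-label study (SAP 3.3 and 3.4). ORR by central read is a secondary endpoint (SAP 2.2.2).

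Under the concordance-rate heading of SAP 9.1, two summaries compare the reads:

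- **Concordance rate.** A confusion matrix over all response categories is produced, and the "concordance rate is calculated by adding the diagonal counts and dividing by the total number of patients assessed".
- **Agreement (%).** The "agreement (%) of the investigator assessment with the central read in terms of best ORR will be calculated". The formula in parentheses is "the total number of patients with a best response of CR or PR by central review divided with the total number of patients with" CR or PR by investigator assessment, multiplied by 100.

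Two rules on missing reads follow: "Patients without any post-baseline response assessment will be considered as not evaluable (NE) in both the central read and investigator assessment", and "Patients who have been evaluated by investigator assessment, but not by central review assessment will be excluded from the concordance analysis".

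Best response is defined over different windows. For the central read (SAP 7.3.4.2) it is the "best response the subject had since treatment started taking into account scheduled and unscheduled visits". For the investigator (SAP 7.3.4.1) it covers the end of Cycles 2 and 3, follow-up assessments, "or at an unscheduled assessment after end of second cycle".

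**The concern.** Agreement on a yes/no classification is a property of pairs: did both reads put this patient in the same class? The SAP's formula uses no paired information. It compares how many responders each read found, not which patients they were.

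This matters because the primary ORR rests on unblinded investigator judgement with no control arm. A report that cites a high agreement with the independent read will be taken as support for that ORR. The concordance rate does not fill the gap exactly, because it runs over all response categories and so counts CR versus PR as a disagreement. The ratio is the only planned summary labelled as agreement on the split that defines the primary endpoint, CR/PR versus not. SAP 7.1 presents summaries by subtype unless stated otherwise, so denominators will be small and one patient can move the figure by many points.

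A second, smaller question is whether patients never assessed, coded NE on both reads, count as concordant.

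**Working it through.** **Inputs.** The formula is from SAP 9.1. The planning case is from SAP 5, which takes the "expected number of responses (9 responses), N=30". The documents give no results for either read, so all other cell counts are assumptions.

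The SAP states no value for this measure, so there is none to reproduce. The planning figures around the borrowed counts do reproduce:

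- Chance of at most 1 response in 10 at a true ORR of 30%: 0.7^10 + 10 × 0.3 × 0.7^9 = 0.149 (stated 14.9%).
- Exact lower 95% limit for 9 of 30: 14.7% (stated 14.7%).

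**Notation.** a = responder on both reads, b = investigator only, c = central only, d = neither, N = a + b + c + d.

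- SAP agreement = (a + c)/(a + b)
- Investigator responses confirmed centrally = a/(a + b)
- Overall responder agreement = (a + d)/N
- SAP agreement minus confirmed share = c/(a + b)

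The SAP figure therefore equals the confirmed share only when c = 0, and it passes 100% as soon as c > b. Adding one central-only responder moves a patient from d to c: the SAP figure rises by 1/(a + b) and overall agreement falls by 1/N.

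**Movement in the wrong direction.** N = 30, a = 7, b = 2 (9 investigator responders):

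| c | d | SAP agreement | Confirmed share | Overall agreement | Kappa |
|---|---|---|---|---|---|
| 0 | 21 | 7/9 = 77.8% | 77.8% | 28/30 = 93.3% | 0.83 |
| 1 | 20 | 8/9 = 88.9% | 77.8% | 27/30 = 90.0% | 0.75 |
| 2 | 19 | 9/9 = 100% | 77.8% | 26/30 = 86.7% | 0.68 |
| 3 | 18 | 10/9 = 111.1% | 77.8% | 25/30 = 83.3% | 0.62 |

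The excess over the confirmed share is 0, 11.1, 22.2 and 33.3 points.

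**Blindness to overlap.** With 9 responders on each read, b = c = 9 − a, and the SAP figure is 9/9 = 100% for every a from 0 to 9. At a = 9 overall agreement is 30/30 = 100%; at a = 5 it is (5 + 17)/30 = 73.3%; at a = 0 it is 12/30 = 40.0%.

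**Undefined case.** If a subtype has no investigator responder, a + b = 0 and the figure cannot be computed.

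**Can c exceed 0 here?** Yes. Two readers can judge the same scans differently. The windows also differ: an unscheduled scan before the end of Cycle 2 can count for the central best response but not for the investigator's.

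**Patients never assessed.** If m such patients are counted as concordant, the rate moves from k/n to (k + m)/(n + m), where k of n assessed patients agree. With assumed counts and n + m = 30:

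| m | Left out | Counted as concordant | Change (points) |
|---|---|---|---|
| 1 | 20/29 = 69.0% | 21/30 = 70.0% | 1.0 |
| 2 | 20/28 = 71.4% | 22/30 = 73.3% | 1.9 |
| 4 | 18/26 = 69.2% | 22/30 = 73.3% | 4.1 |
| 6 | 17/24 = 70.8% | 23/30 = 76.7% | 5.8 |

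The starting rates differ slightly because counts are whole numbers. At m = 4, a start of 16/26 = 61.5% goes to 20/30 = 66.7%, and 21/26 = 80.8% goes to 25/30 = 83.3%.

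**The case against.** The strongest reply is that the SAP discloses its formula and speaks of agreement in terms of ORR. On a common denominator the figure is the ratio of the two ORRs, a legitimate aggregate check for inflation of the investigator's rate. The same paragraph plans a confusion matrix, from which anyone can rebuild the paired measures. On that view the fault is one word.

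Much of this stands. A ratio of ORRs is worth reporting, and patient-level disagreement will be visible in the cross-table. But a ratio of rates is not agreement, and disclosing the formula does not make the label true. The common denominator is not secured either: the exclusion of patients without a central read is stated for the concordance analysis, and the SAP does not say clearly that it also governs the ratio.

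Other points limit the size of the finding:

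- The excess of 0 to 33 points is measured against the confirmed share. Against overall agreement the SAP figure is lower in two of the four scenarios (78% versus 93%, and 89% versus 90%).
- The perverse movement comes from added central-only responders. Starting from equal totals, extra investigator-only responders, the likelier direction of bias in an open-label study, lower the ratio as they should.
- Zero overlap is an algebraic extreme. Both reads apply the same response criteria.
- The early-scan route is narrow. No response scan is scheduled before Cycle 2 Day 28 (Protocol 10.2 and Table 2). Ordinary reader disagreement is the more likely source of central-only responders.
- The point on never-assessed patients depends on the reading. A denominator of patients assessed can naturally leave them out, whereas the closing reference in SAP 9.1 to the ITT population, if it covers this analysis, points the other way. Protocol 10.6 asks for an evaluation after early discontinuation if possible, which should keep their number small.

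**Conclusion.** The concern holds. The quantity labelled agreement is a ratio of responder totals. It cannot distinguish full overlap from none, it is not bounded by 100%, and it increases with every central-only responder. These properties follow from the formula and do not depend on the assumed counts; only the sizes do. In a 30-patient subtype with 9 investigator responders, each central-only responder adds 11 points to the figure and takes about 3 points off overall responder agreement.

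The consequence is confined to a supportive analysis. The primary ORR, its exact interval, the central-read ORR, the confusion matrix and the concordance rate are not affected by the ratio. The treatment of never-assessed patients is a lesser point: it touches only the concordance rate, only under one reading, and by about 1 to 6 points under the counts assumed.

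The text should be corrected, but it does not threaten the trial's main result.

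**What to change.** In SAP 9.1, replace the ratio with three paired measures from the planned confusion matrix, collapsed to CR/PR versus not, among patients with both reads:

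1. the share of investigator responders confirmed by central read, a/(a + b);
2. the share of central responders also called by the investigator, a/(a + c);
3. overall percent agreement, (a + d)/N.

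Alternatively, keep the ratio, rename it as the ratio of central to investigator responder counts, and state that both counts come from the same patients. In either case, say what is reported when a denominator is zero.

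Add one sentence that patients with no post-baseline assessment are left out of both numerator and denominator of the concordance rate, with their number reported separately.

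The cost is SAP wording and a small change to table programming. The confusion matrix already holds the counts, and neither the sample size nor the primary analysis changes. The confirmed share can never be higher than the present ratio, so the reported figure may drop; overall agreement may be higher or lower than the ratio.

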6. ANALYSIS POPULATIONS

The following analysis populations will be defined:

- Intent-to-treat (ITT) Population: Consists of all patients who received at least one dose of study drug. Patients without any post baseline assessment of NHL response will be included as non responders.
- Safety Population: Consists of all patients who received at least one dose of study drug.
- Pharmacokinetic (PK) Population: The Pharmacokinetic Population will include all patients who have at least one quantifiable serum MOR00208 concentration. (PK parameters will be calculated as data permit.)

Please note that the definition of the PK population differs slightly from that in the protocol: see section 12.

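### Patients with no post-baseline assessment are coded NE on both reads and so count as agreement, which inflates the central-versus-investigator concordance rate

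*SAP*

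**What the plan says.** SAP 9.1, under the concordance rate, defines the measure as "the number of patients that are concordant over the total number of patients assessed, and will be calculated across all response categories". The computing rule is that the "concordance rate is calculated by adding the diagonal counts and dividing by the total number of patients assessed".

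Two rules on missing reads follow. The first is "Patients without any post-baseline response assessment will be considered as not evaluable (NE) in both the central read and investigator assessment". The second is "Patients who have been evaluated by investigator assessment, but not by central review assessment will be excluded from the concordance analysis". No other exclusion is stated.

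The population is ITT. SAP 9 sets this for all efficacy analyses, and the paragraph on central-review coverage that closes 9.1 repeats it: "The analysis will be conducted using the ITT population". SAP 6 defines ITT by dosing alone: "Consists of all patients who received at least one dose of study drug". A post-baseline assessment is not required.

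The two response scales differ. The investigator scale in SAP 7.3.4.1 has CR, PR, SD, PD and "Missing (if response assessment is not done"); it has no NE category. The central scale in SAP 7.3.4.2 does have one: "NE - Non-Evaluable (can be applied if repeated measurements cannot be applied for reasons such as inadequate or missing imaging".

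**The concern.** A concordance rate should say how often two readers agree when both have read the same patient. Here a patient with no reading from either side is given the same code twice and so lands on the diagonal. Because the investigator scale has no NE category, the coding rule itself creates the match.

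Such patients are foreseeable. The first scheduled response assessment is Cycle 2 Day 28 (Protocol 10.2 and Table 2). At the end-of-study visit, response is assessed by physical examination only (Protocol 10.5). For a patient who leaves before any response assessment, later evaluation is sought only if possible (Protocol 10.6). Some early leavers are replaced (Protocol 9.11.1), but ITT keeps everyone who was dosed. The SAP expects the group: it counts them as non-responders for ORR and plans a sensitivity ORR without them.

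The primary ORR is investigator-assessed in an open-label, single-arm trial. The concordance rate is the only planned patient-level agreement rate between that assessment and the central read. The separate CR/PR agreement percentage divides one total by another, so it could be 100% even if the two sides named different responders. Early drop-out should not make the patient-level rate look better.

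**Working it through.** **No figure to reproduce.** The documents state no concordance rate or target and no expected number of unassessed patients. The check is therefore algebra, with assumed values put in.

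**Inputs**
- n = patients assessed on both reads; a = agreements among them; c = a/n, the true concordance.
- u = ITT patients with no post-baseline assessment, placed in NE/NE by SAP 9.1.
- N = n + u, leaving aside investigator-only patients, whom SAP 9.1 excludes. The study enrols 40 to 120 patients (SAP 5).

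**Formulas**
- Rate as planned, with NE/NE in numerator and denominator: (a + u)/(n + u).
- Rate among patients read by both: a/n = c.
- Difference: (a + u)/(n + u) − a/n = [u/(n + u)] × (1 − c).

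The difference is positive whenever u > 0 and c < 1.

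**Results** (every u and a is an assumption)

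| N | u | a/n | As planned | Inflation (points) |
|---|---|---|---|---|
| 120 | 10 | 66/110 = 60.0% | 76/120 = 63.3% | 3.3 |
| 120 | 20 | 60/100 = 60.0% | 80/120 = 66.7% | 6.7 |
| 120 | 12 | 76/108 = 70.4% | 88/120 = 73.3% | 3.0 |
| 120 | 24 | 67/96 = 69.8% | 91/120 = 75.8% | 6.0 |
| 30 | 6 | 17/24 = 70.8% | 23/30 = 76.7% | 5.8 |
| 10 | 2 | 5/8 = 62.5% | 7/10 = 70.0% | 7.5 |

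The last two rows match the planned sizes of a full cohort and of one stopped after Stage 1. They matter because SAP 9.2 asks for results by subtype unless otherwise specified.

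**Range.** With 5% unassessed and 90% concordance: 0.05 × 0.10 = 0.5 points. With 20% unassessed and 50% concordance: 0.20 × 0.50 = 10 points.

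**The denominator.** The rate is divided by patients assessed, yet the coding rule keeps patients who were not. There are three ways to resolve this:
1. Keep them in numerator and denominator, as in the table.
2. Remove them from both. There is then no inflation, but the NE sentence plays no part in the calculation.
3. Keep them in the numerator only, giving (a + u)/n. This can exceed 100%: with N = 120, u = 18, a = 92, it is 110/102 = 107.8%.

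None of the three is both coherent and faithful to every sentence, so the wording needs repair whichever was meant.

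**The case against.** The strongest objection is that the SAP never says in words that NE/NE is an agreement. If patients assessed governs both numerator and denominator, nothing is inflated, and the NE sentence could serve only to account for every ITT patient in the displayed matrix. That reading is possible. But the diagonal rule exempts no cell, and the sentence after the NE rule excludes a different group and leaves these patients in. A programmer following the text would count them.

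It can also be said that the measure is descriptive, that no decision depends on it, and that the matrix would let a careful reader subtract the NE/NE cell. All of this stands and limits the consequence, but the headline rate would still be too high. The planned coverage figure, the share of investigator-assessed patients with at least one central review, already shows most of what is needed on investigator-only patients. It does not show how many were never assessed.

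Four stronger readings are tempting, and the documents do not support them:
- A reader might infer that concordance is the plan's main evidence for the investigator's assessment. Central-read ORR is a named secondary endpoint, and all efficacy analyses are run on both reads.
- A reader might infer that the handling of missing reads as a whole pushes the rate upward. Only the NE/NE rule has a known direction. Dropping investigator-only patients could move the rate either way, and the fix below drops them too.
- A reader might take the 20-of-120 example with a literal denominator and report 80/100 = 80%. That is the numerator-only reading, which is incoherent and not a likely computation.
- A reader might infer that the rate follows drop-out instead of reader agreement. It rises with both; with 20 of 120 unassessed, the weight on true concordance is still 100/120 = 0.83.

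**Conclusion.** The concern holds for the category concordance rate in SAP 9.1. On the plain reading, patients whom nobody assessed count as agreements, and the rate is too high by (share unassessed) × (1 − true concordance). The direction is certain if any patient is unassessed and agreement is below 100%.

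The size cannot be taken from the documents. About 0.5 to 10 points rests on assuming 5–20% unassessed and 50–90% true concordance; about 3 points corresponds to 10% unassessed and 70% concordance. The planned attempt to evaluate early leavers about a month after discontinuation would reduce the number unassessed.

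The investigator ORR, the central ORR, the ORR sensitivity analysis and the CR/PR agreement percentage do not use the NE/NE cell and are unaffected. Counting unassessed patients as non-responders in ORR is a separate rule and is not questioned here. This is a correction to a supporting statistic; it casts no doubt on the primary result.

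**What to change.** In SAP 9.1:
1. Restrict both numerator and denominator of the concordance rate to patients with at least one post-baseline assessment on both reads.
2. Replace the rule that codes unassessed patients NE on both sides. Keep NE in the matrix only where a reader reviewed a scan and called it non-evaluable.
3. Report beside the rate the number of patients never assessed and the number with an investigator read only.

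The cost is a change of wording and one programming condition. The condition is already largely specified, because the sensitivity ORR selects patients with at least one post-baseline assessment and is run on each read. The downside is that the reported concordance will be slightly lower.
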